To establish the feasibility of completing the Catherine Bergego Scale (neglect) (Azouvi et al., 1996), Scale for Contraversive Pushing (SCP) (Karnath et al., 2002) and bucket test (SVV) (Zwergal et al., 2009) in a clinical environment with acute stroke patients to assist with identification of vertical perception loss.

The secondary research questions that this study will aim to address are:

- What percentage of patients admitted to an acute stroke unit show a positive test for vertical perception loss within four weeks of admission (evidence of subjective visual vertical (SVV) tilt on either bucket test or Catherine Bergego Scale or evidence of subjective postural vertical (SPV) tilt on SCP)
- For those able to complete the assessments, does vertical perception loss show any relationship with:
 - Discharge (DC) destination
 - Care package size on discharge
 - Number of inpatient falls
 - Level of functional independence on discharge
- Is there a trend for any element of the SCP or the Catherine Bergego to be more correlated with SVV tilt.

2. Objectives and outcome measures.

Primary objective:

To establish the feasibility of completing the Catherine Bergego Scale, the Scale for Contraversive Pushing (SCP) and the bucket test in a clinical environment with acute stroke patients, to assist with identification of vertical perception loss.

Primary outcomes:

The primary outcome is to understand the feasibility of completing the suite of outcome measures in an acute stroke setting:

- Proportion (%) of patients on whom the assessments are attempted.
- Percentage of patients who are able to complete all three assessments within four weeks of admission.
- Time taken to complete the three measures in an acute clinical setting
- A recommendation regarding the most feasible time point to complete these assessments.

Secondary outputs:

The secondary aims are to gain a further understanding of vertical perception loss in acute stroke patients.

- An understanding of factors that prevent or facilitate completion of these three assessments
- An understanding of healthcare professionals' experiences of completing these assessments in an acute stroke unit.
- An understanding of whether people with stroke (or their advocates) find it appropriate to complete all three assessments in an acute stroke setting.
- Percentage of patients admitted to an acute stroke unit showing a positive test for vertical perception loss within four weeks of admission.

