	Patients with pre-morbid visual impairment that will not allow them to see the bucket test. Glasses can be worn.
	Inability to speak the English language and no interpreter can be found

6. Trial Procedures

Recruitment

All patients admitted to an acute stroke unit, who meet the inclusion criteria, may be invited to participate. Potential participants will be identified during the daily handover by members of the clinical or research team. Those meeting the inclusion criteria will be approached by a member of the research or clinical team and invited to participate. This will take place between 48 hours and one week after admission. Potential participants will be provided with the participant information sheet (PIS) regarding this study. If the patient is unable to consent due to cognitive or language impairment or low level of consciousness then their advocate will be approached. Where possible potential participants will be supported to consent using information in different formats (e.g.

through use of pictures) or the skill of appropriate members of the clinical team (e.g. speech and language therapists).

The number of people admitted to hospital with stroke who have language or cognitive impairments that may prevent them being able to consent is substantial. To exclude these potential participants would significantly impact the validity and generalisability of the results. Especially as those with significant strokes are more likely to present with vertical perception loss as well as cognitive and language impairment. If they were excluded a large number of patients with vertical perception loss may not be identified. These groups are often underrepresented in stroke research. If someone is unable to consent an advocate will be approached to consent on their behalf.

Those taking consent will decide on capacity. This includes the chief investigator and the stroke research nurse. Both have significant experience working with people with stroke. Both have undergone Good Clinical Practice training and Mental Capacity Act Training. If in any doubt about capacity other members of the healthcare team (e.g., Speech and Language Therapists) can give advice as to whether the potential participant has capacity or whether their advocate should be approached.

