Participants will only be enrolled in the research if an advocate can be found to consent on their behalf. If someone lacks capacity and does not have an advocate they will be ineligible for inclusion in the research. Advocates will be identified through the medical records of the potential participant and will usually be their next of kin or other named contact. They will only be able to consent once they have read a PIS and had time to ask questions of the research team.

On reading the PIS if the patient or their advocate is willing to participate then they will be asked to sign a consent form, by the research team or chief investigator. Potential participants will have a minimum of 12 hours to read the PIS.

If a participant who lacked capacity, and was consented by an advocate, regains capacity then their informed consent to continue will be sought.

Study protocol

For those patients who consent, the qualified physiotherapists or occupational therapists on the stroke unit, will then attempt to complete all 3 outcome measures with the patient (see assessors and outcome measures below). If the patient is unable to complete any elements of the outcome measure for any reason, this will be recorded. If the patient is unable to complete the outcome measures, then an attempt will be made to complete the outcome measures at 1 week post

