admission, if still unable they will be attempted again at 2 weeks and 4 weeks post admission. At the point participants complete all 3 outcome measures or at 4 weeks (whichever is earliest) most will have no further active participation in the quantitative part of the study. The assessments do not need to all be completed in one sitting and can be spread across sessions. If a patient is unable to be consented at 48 hours they will be consented as soon after this point as possible up to one week after admission, and this will be recorded. If patients are discharged or have a change in status following consenting to participate but prior to completion of the outcome measures any data collected to date will be utilised in the study results and the reasons for non-completion of the outcome measures will be noted as this will inform the feasibility of these outcome measures. The length of time taken to complete the measures will be recorded by the administrator. The expectation is that administration of all three outcome measures will take no longer than one hour. Due to the observational nature of the SCP and Catherine Bergego Scale elements of these can be completed during therapy sessions. The results and implications of the results of the outcome measures will be discussed with the patient or their advocate should they wish. The impact of the results on the therapists will be explored in a focus group.

At the point the participants are discharged from the stroke unit (this could include but not be restricted to: transfer to another rehabilitation facility, to undergo further neurological observation or intervention, discharge home, to undergo further unrelated medical interventions) their notes will be accessed and the following data extracted:

- Demographic details (age, gender)
- Type and location of stroke
- NIHSS on admission
- Number of in-patient falls
- Discharge (DC) destination
- Level of care required on DC – either care home or size of care package
- Functional ability on DC using the Modified Rankin Scale (MRS) (van Swieten et al., 1988) and the Barthel Index (Mahoney and Barthel, 1965) as these are routinely collected for all patients
- Amount of physiotherapy and occupational therapy received during inpatient stay as submitted to the Sentinel Stroke National Audit Programme (SSNAP). This includes minutes of therapy received per session of therapy, number of sessions of therapy per day and number of days on which therapy was received

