will be calculated. Demographic data of the participants will be tabulated for display including: number of patients with left or right stroke, number of patients with haemorrhage or infarct stroke, female/male/non-binary/other gender, mean length of stay, location of stroke, median NIHSS on admission, median MRS and Barthel Index on discharge, place of discharge (home/care home/other), care needs on discharge (nil, one, two, three or four calls per day or 24 hour and number of carers required), number of in-patient falls, median minutes of therapy per day (for OT and Physiotherapy) and median number of days on which OT and Physiotherapy were received.

The main outcome will be the percentage of consenting patients who are able to complete the three outcome measures within four weeks of admission. The percentage of patients able to complete each of the outcome measures individually will be calculated to see if one of the outcome measures is more feasible than the others. Reasons for non-completion will be collated for each of the outcome measures and presented using an appropriate tool. The mean time and standard deviation (SD) to complete all three and each individual outcome measure will be presented. To identify the most feasible time point to complete the outcome measures median (and confidence intervals) time to completion of each outcome measure and time to completion of all three outcome measures will be calculated. The percentage of participants completing each or all of the measures at 48 hours, 1 week, 2 weeks and 4 weeks will be presented.

The median scores and confidence intervals for the SCP and Catherine Bergego scale will be calculated, as well as the mean and SD for the bucket test. The percentage of patients with vertical perception loss will be reported – this will be defined as a positive test on one or more of the measures (SVV >2.5°, Catherine Bergego Scale >1, SCP >0.5). For each patient it will be noted if they test positive on one, two or all three measures. This will assist in informing which of the measures will be required in future studies.

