To identify trends for vertical perception loss and discharge status narrative statistics will be utilised. For instance the numbers of participants identified as having vertical perception loss who are discharged home will be investigated. If possible a Spearman Rank Correlation with Fisher-Z between outcome measure score and discharge information (e.g. length of stay in days, MRS score or Barthel Score) will be used. These tests have been chosen as the data is ordinal and are expected to be non-

parametric in nature. An ordinal regression will allow identification of which outcome measure is most likely to relate to discharge information.

A Spearman Rank Correlation with Fisher-Z will be completed on each element of the SCP and Catherine Bergego Scale against SVV to identify if any specific elements of the measures are more indicative of vertical perception loss than others. An ordinal regression will allow identification of which elements of the SCP and Catherine Bergego Scale are most likely to relate to SVV tilt.

The percentage of patients able to complete the measures, along with scores and confidence intervals for the outcome measures will be used to determine potential sample size for larger trials (Eldridge et al., 2016) and assess the change in vertical perception loss during in-patient admission.

It is known that neglect (Esposito et al., 2021) and pushing behaviour (Dai et al., 2022) improve over time. Therefore, changes in a sub-sample of the population will be tracked to inform future interventional research. For the subsample who have outcomes taken on discharge a Wilcoxon Sign Rank test will be used to identify the change in scores of the measures during in-patient stay. This will be completed for the whole study population and for each of the subgroups defined as mild, moderate or severe vertical perception loss.

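### Correlating scores taken anywhere from 48 hours to 4 weeks with total length of stay can produce a spurious correlation of either sign

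*Combined protocol and SAP*

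**What the plan says.** Section 8 (Statistics and Data Analysis) plans, where feasible, a "Spearman Rank Correlation with Fisher-Z between outcome measure score and discharge information (e.g. length of stay in days, MRS score or Barthel Score"), followed by an ordinal regression to see which measure relates most to discharge information. It gives no landmark, stratification or adjustment for the day on which the score was obtained, and it does not say from when stay is counted.

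The secondary research questions at the end of Section 1 restrict the relationship question to completers: "For those able to complete the assessments, does vertical perception loss show any relationship with" the listed discharge outcomes.

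Section 6 (Study protocol) lets the time of scoring vary. Patients who fail are retried at 1 week; "if still unable they will be attempted again at 2 weeks and 4 weeks post admission". Section 8 confirms the range: "The percentage of participants completing each or all of the measures at 48 hours, 1 week, 2 weeks and 4 weeks will be presented".

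For patients discharged early, Section 6 keeps partial results: "prior to completion of the outcome measures any data collected to date will be utilised in the study results".

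Two statements bear on the direction of any bias. Section 6 (Recruitment) says "those with significant strokes are more likely to present with vertical perception loss as well as cognitive and language impairment". Section 8 says that neglect and pushing behaviour get better with time.

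**The concern.** A score obtained at a given visit exists only if the patient was still on the unit at that visit. On the natural reading, stay runs from admission, so the days spent waiting to become testable are counted as part of the outcome. This is guaranteed (immortal) time, or left truncation. A similar patient who leaves before becoming testable on that measure contributes no score for it.

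If the score is also related to when it was obtained, it inherits a correlation with stay that says nothing about vertical perception and prognosis. Section 1 already expects neglect and lateropulsion to mean longer rehabilitation, so a positive artefact would look like confirmation. If stay is used in the ordinal regression, the comparison between measures could be distorted too, because the measures may be completed on different days. As a bias, it does not shrink with more patients.

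**Working it through.** The plan gives no target correlation, power or significance level for this analysis, so there is no figure to reproduce. The check is a structural argument followed by a simulation with a true correlation of zero.

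**Structure.** Let S be the score, C the day the measure is completed and T the stay from admission. A pair (S, T) is observed only if T ≥ C.
- From the documents: stay exceeds 72 hours (Section 5), and attempts fall at about 48 hours, then at 1, 2 and 4 weeks (Sections 6 and 8). The minimum possible stay among those scored is therefore about 3, 7, 14 and 28 days by visit.
- If S is unrelated to both C and T, selecting on T ≥ C leaves S unrelated to T. Truncation alone creates no correlation.
- If S is related to C, then among those with T ≥ C a later C goes with a longer T, and S picks up a correlation with T of the same sign as its relation to C.

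**Assumed inputs (none are in the documents).**
- Stay is log-normal, median 7, 14 or 21 days, log-SD 0.8, restricted to more than 3 days, and independent of severity and of completion time.
- Completion falls on day 3, 7, 14 or 28; 40% to 80% complete at the first visit and 3% to 10% never do.
- g is the latent correlation of severity with later completion: 0, 0.3, 0.6 or 0.9.
- Recovery is the fall in score per log unit of time: 0, 0.3, 0.6 or 1.0 SD.

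**Spearman rho among scored patients (true value 0; 400,000 patients per scenario).**

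| Setting | rho |
|---|---|
| g = 0, no recovery | 0.00 in all nine settings |
| g = 0.3, no recovery | +0.02 to +0.07 |
| g = 0.6, no recovery | +0.04 to +0.16 |
| g = 0.9, no recovery | +0.06 to +0.28 |
| g = 0, with recovery | -0.01 to -0.19 |
| g = 0.6, recovery 0.6 | -0.01 to +0.02 |
| g = 0.6, recovery 1.0 | -0.09 to -0.01 |

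The first-attempt completion rate matters. With 80% completing at the first visit, even g = 0.9 without recovery gives only +0.09, +0.08 and +0.06 at median stays of 7, 14 and 21 days.

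**Scale.** The correlation needed for two-sided p < 0.05 by Fisher-Z is tanh(1.96/√(n-3)):
- n = 24: tanh(1.96/√21) = 0.40
- n = 50: tanh(1.96/√47) = 0.28
- n = 100: tanh(1.96/√97) = 0.20
- n = 250: tanh(1.96/√247) = 0.12

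False-positive rates were simulated for 100 enrolled, about 60 scored, median stay 10 days, 40/60/75/85% able by days 3/7/14/28 and no recovery. Two ways of modelling the severity-delay link were used. A nominal 5% test of the planned correlation was significant in 7% to 12% of trials with a weak link, 14% to 26% with a medium link and 37% to 43% with a strong link.

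**Alternatives under the same null.**
- Correlation within completion visit: rho -0.006 to +0.007.
- Cox model with delayed entry at the completion day: about 4% to 8% rejection at a nominal 5%.
- Stay counted from the test date: rho -0.11 to +0.05 across the settings tried.

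**The case against.** A reader might infer that the correlation must come out positive. The documents do not support that. Truncation alone gives zero. A positive value also needs higher scorers to complete later, and Section 6 supports this only qualitatively, in an argument about consent that does not mention completion times. Section 8's own statement about recovery pulls the other way. The sign is open, and the two forces may cancel. This objection stands in full, but it does not rescue the plan: an unbiased result would depend on two unknown quantities offsetting each other.

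Further objections, and what stands of them:
- *The target is peripheral.* Stay is one example within an analysis done only if possible. It is not among the relationships listed in Section 2, and guaranteed time does not enter the Modified Rankin Scale or Barthel Index. This stands and limits the importance of the point.
- *The false-positive rates apply a rule the plan does not state.* True; no significance level is given. They illustrate size only.
- *Low first-attempt completion is an unfavourable assumption.* Fair. The Catherine Bergego Scale and the Scale for Contraversive Pushing are observational, so delay may affect the bucket test most, and the bias is small when most patients complete early.
- *Early leavers are not wholly lost.* Correct. Partial data are kept, so the problem must be judged measure by measure.
- *Counting from admission is inferred.* Also correct. The undefined origin is itself something to settle.

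**Conclusion.** The point holds in a limited form. As planned, the score-versus-stay correlation can be spurious because assessment time varies and a late score requires a long stay. The bias exists only if score and completion time are related, and its direction cannot be fixed from the documents. Under the assumed inputs the null correlation ranges from about -0.19 to +0.28, with values near zero when most patients complete at the first attempt or when delay and recovery offset each other. These figures rest on assumed distributions of stay, completion rates, severity-delay links and recovery rates, and on reading stay as counted from admission. The percentage completing all three measures, which is the main outcome, is untouched. It is worth correcting because the change is small and the artefact could be mistaken for a prognostic finding.

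**What to change.** Add to Section 8:

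> *Stay is counted from admission. For each measure separately, time to discharge will be analysed with each participant entering on the day that measure was completed (delayed entry).*

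Alternatively, calculate the score-stay correlation within completion visit (48 hours, 1, 2 and 4 weeks). Do not rely on stay counted from the test date alone.

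The cost is a sentence or two and no new data: Section 8 already needs time to completion for each measure and already plans to report completion by visit. The downsides are modest. Late-visit strata will be small, and delayed entry is less familiar to readers than a simple correlation.
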